6.9 Clinical Outcome Assessments

Identifying measures to evaluate cognition and behavior in children with IDD and DS specifically, within clinical trials has traditionally been challenging.¹⁰ Leading clinician and scientist experts were assembled by the NIH to review existing measures and identify those that are appropriate for clinical trials in individuals with IDD and specifically DS.¹¹ The ABC, ESS-CHAD, and CSHQ will be collected using Electronic Participant Reported Outcomes (ePRO), see Section 15.3. Details regarding which individual(s) complete(s) each measure at the various visits are included in [Table 2](#).

Table 2. Frequency of measures and who completes each measure.

Measure	Frequency Parent/ Legal Guardian Completes	Frequency Clinician Completes
ABC (Section 0)	Screening, Week 4, Week 8, Early Withdrawal	N/A
Sleep Assessments (Section 6.9.2)	Day 1, Week 4, Week 8	N/A
CGI-I (Section 6.9.3)	N/A	Weeks 1-8, Early Withdrawal
CGI-S (Section 6.9.3)	N/A	Screening

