10.4 Analysis Plan

Descriptive statistics, such as number of observations, mean, median, SD, standard error, minimum, and maximum, will be presented for continuous variables (e.g., age, weight, etc.). Other descriptive statistics, such as counts, proportions, and/or percentages, will be presented to summarize discrete variables (e.g., race, sex, etc.). All descriptive analyses will be presented by appropriate treatment group and overall. A 95% confidence level will be used for confidence intervals. A detailed description of statistical methods and secondary analyses will be prepared and presented in the statistical analysis plan prior to data lock for final analyses.

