10.4.1 Primary Analysis

The primary objective of this study is to determine GIR efficacy for the treatment of hyperactivity, inattention, and impulsivity in children with DS using the ABC-H scale. This objective will be evaluated using the endpoint of change from baseline to Week 8 of the ABC-H subscale score. The ABC-H subscale is a continuous scale with a minimum score of zero to a maximum score of 48, so the primary analysis will be conducted assuming a normal distribution. A mixed effect model analysis will be conducted to compare the change in ABC-H subscale score from baseline. Analysis will be conducted in SAS statistical analysis software using a PROC MIXED procedure. Fixed effects in the model will include indicator for the treatment assignment (GIR vs. placebo), baseline ABC-H score, and assessment week. To account for the correlation of longitudinal scores collected at baseline, Week 4, and Week 8, a participant level random intercept will be included in the model. The primary endpoint (effect size, p-value, and 95% confidence interval) of difference in the change from baseline to Week 8 of the ABC-H subscale will be evaluated using a contrast statement in the model. Additional analysis to evaluate impact of other covariates, including age, sex, weight, comorbid diagnosis of ASD, use of alternative agent(s) to treat ADHD, site, cumulative dose, demographics, may also be conducted. A sensitivity analysis may also be performed to determine how the missing data mechanism affects the primary outcome results.

Secondary efficacy outcome measures: GIR effectiveness for the treatment of hyperactivity, impulsivity, and inattention in children with DS will also be assessed using change from baseline to Week 4 of the ABC-H subscale score and with the CGI-I specific to hyperactivity, inattention, and impulsivity behaviors. The change from baseline to Week 4 of the ABC-H subscale score will be analyzed using the mixed effects model described above. The CGI-I is measured on a 7 point Likert scale from “very much improved” to “very much worse.” The proportion of participants with a CGI-I of “1-very much improved” or “2-much improved” will be analyzed as a dichotomous outcome. These dichotomized outcomes will be analyzed using a generalized linear mixed model with binary distribution and logit link. All mixed models for secondary efficacy endpoints will include covariates identified above for the analysis of primary efficacy endpoint.

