10.6 Sample Size Considerations

The primary hypothesis is that change from baseline on ABC-H subscale over the 8-week trial will be greater in GIR compared to placebo. In a randomized clinical trial of GER in ASD,¹⁵ the guanfacine group showed a 43.6% decline in scores on the ABC-H subscale (mean scores of 34.2 at baseline to 19.3 at week 8 visit) compared with a 13.2% decrease in the placebo group (mean scores of 34.2 at baseline to 29.7 at week 8 visit; effect size Cohen's $d=1.67$). Modal doses of GER in this trial were 3 mg/day (range 1 mg/day to 4 mg/day). In another single arm GIR trial,⁶ Capone et al. reported a mean decline in ABC-H scores from baseline to follow-up of 25% (mean scores of 29 at baseline to 21.2 at follow-up visit, Cohen's $d = 0.9$) over an average of 21 weeks. Average doses of GIR in the Capone study were 1.1 (± 0.5) mg/day, reflecting the more conservative approach to dose escalation in this patient population with DS. A decline in the ABC-H scale scores in the guanfacine group ranged from 25% to 43% across these studies. Although there are no identified studies characterizing a "clinically meaningful change" in ABC-H scores, the open-label Capone study revealed a significant improvement in target behaviors characterized as "inattention" and "activity" with the associated 25% improvement in ABC-H scores.⁶

Based on these studies, a conservative effect size of Cohen's $d = 0.9$ was assumed for the current randomized trial, which will be equivalent to assuming a 31.3% decline in the guanfacine arm (mean scores of 30 at Baseline to 20.6 at Week 8, $SD = 6$) compared with a 13.3% decrease in the placebo arm (mean scores of 30 at Baseline to 26 at Week 8, $SD = 6$). A sample size of 48 will achieve greater than 80% power to reject the null hypothesis of zero effect size when the population effect size is 0.90 and the significance level (alpha) is 0.050 using a two-sided two-sample equal-variance t-test. If a 20% dropout is assumed, N=60 participants will need to be enrolled.

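### The primary mixed model gives baseline ABC-H two roles, as a repeated response row and as a covariate; depending on how it is coded, the Week 8 effect is diluted, its standard error is too small, or the baseline adjustment is lost

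*Combined protocol and SAP*

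**What the plan says.** Section 10.4.1 sets out the primary model in a few sentences.

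- Response: "A mixed effect model analysis will be conducted to compare the change in ABC-H subscale score from baseline".
- Fixed effects: "Fixed effects in the model will include indicator for the treatment assignment (GIR vs. placebo), baseline ABC-H score, and assessment week". No treatment-by-week term is listed.
- Repeated rows and correlation: the model is to handle "longitudinal scores collected at baseline, Week 4, and Week 8, a participant level random intercept will be included in the model".
- Primary result: the "difference in the change from baseline to Week 8 of the ABC-H subscale will be evaluated using a contrast statement in the model".

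Table 2 in section 6.9 gives the ABC schedule as "Screening, Week 4, Week 8, Early Withdrawal", so there is one pre-treatment score and two scheduled scores on treatment. Section 10.4 leaves further detail for later: "A detailed description of statistical methods and secondary analyses will be prepared and presented in the statistical analysis plan prior to data lock". No separate SAP text is among the documents reviewed.

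**The concern.** A change from baseline is zero for every child at baseline. If that row is kept in the response, it has no variance and no correlation with later rows. If the response is instead the raw score, the baseline row equals its own covariate. A random intercept assumes one variance and one correlation across all rows, and these three rows cannot satisfy that.

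The primary estimate, confidence interval and p-value all come from this model. Section 10.4.1 also uses it for the secondary Week 4 ABC-H endpoint, and section 10.4.3 analyses the sleep scales in a similar way. At stake is whether the reported effect is the Week 8 effect, and whether its test keeps the nominal 5% level.

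**Working it through.** **Inputs from the protocol.** Week 8 means 20.6 (GIR) and 26 (placebo), SD 6, two-sided alpha 0.05, 48 evaluable children, 20% dropout (section 10.6); 2:1 allocation (section 4.2.1), hence 32:16.

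**Assumed, because the documents give no figure.** Visit correlations: equal at 0.3, 0.5 or 0.7, plus unequal patterns with values up to 0.8. Week 4 effect: 5.4 or 2.7 points. Data are complete. Effects are shown as absolute sizes.

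**1. The plan's own figure.** (26 − 20.6)/6 = 0.90. A two-sample t-test at 32:16 has 82.1% power, and 48/0.8 = 60. Both stated figures reproduce. They come from a t-test, so the points below do not change them.

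Below, σ² = 36 and k = 1/32 + 1/16 = 0.09375.

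**2. Listed fixed effects only, baseline row kept.** The treatment coefficient is the average of the three row differences, (0 + d4 + d8)/3.
- d4 = d8 = 5.4: 10.8/3 = 3.6.
- d4 = 2.7, d8 = 5.4: 8.1/3 = 2.7.

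Simulation (4,000 trials per setting) agrees. The model SE divided by the true SD is 0.97–1.03 and null rejection is 3.8–5.8%, so the SE is valid for this diluted quantity. Coverage of the true 5.4 is only 6–57%.

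**3. Treatment-by-week added, Week 8 level difference tested.** Take all correlations as 0.5 and the response as change. The single baseline slope averages over the rows: (0 − 0.5 − 0.5)/3 = −1/3.
- Residual variance of the baseline row: 36 × (1/3)² = 4.
- Residual variance at Week 4 and at Week 8: 36 × (1 + 4/9 − 2 × 2/3 × 0.5) = 28.
- Variance the model pools: (4 + 28 + 28)/3 = 20.
- Model SE √(20k) = 1.37; true SD √(28k) = 1.62; ratio 0.845.

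Simulation gives 1.38 against 1.63–1.64. Over the 4,000-trial settings the ratio is 0.81–0.87 and null rejection 8.4–10.5%. Further runs of 1,500 trials, including correlations up to 0.8, reach 12.4%. The estimate is unbiased (5.34–5.43).

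**4. Treatment-by-week added, baseline-to-Week 8 contrast tested.** The baseline covariate is constant within a child, so with complete data it drops out of this contrast. The true variance is 2σ²(1 − ρ)k, with ρ the baseline–Week 8 correlation. The model replaces (1 − ρ) by its average over the three visit pairs.
- Equal correlations of 0.5: √(2 × 36 × 0.5 × k) = 1.84 (simulated model SE 1.83). The covariate-adjusted SE is √(36 × 0.75 × k) = 1.59 (simulated 1.60). The variance ratio is 2/(1 + 0.5) = 1.33. Null rejection over the equal-correlation settings is 4.4–5.3%.
- Baseline–Week 4 0.5, baseline–Week 8 0.4, Week 4–Week 8 0.7: the average of (1 − ρ) is (0.5 + 0.6 + 0.3)/3 = 0.467. Model SE is 1.77 against a true SD of √(2 × 36 × 0.6 × k) = 2.01, a ratio of 0.88. Simulated null rejection is 8.7%; other unequal patterns gave up to 8.9%.

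**5. Rows Week 4 and Week 8 only, baseline as covariate, treatment-by-week.** Mean estimate 5.34–5.43; null rejection 4.2–5.5%. One extra run of 1,500 trials at correlations 0.7, 0.6 and 0.8 (same order as in step 4) gave 6.1% (Monte Carlo SE about 0.6 points), and another run at the same setting gave 5.3%. Without treatment-by-week, the coefficient is (2.7 + 5.4)/2 = 4.05 when the Week 4 effect is half.

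| Coding | Estimate of a true 5.4 | Null rejection |
|---|---|---|
| Listed terms, baseline row kept | about 3.6 or 2.7 | 3.8–5.8% |
| With treatment-by-week, Week 8 level | unbiased | about 8–12% |
| With treatment-by-week, baseline-to-Week 8 | unbiased | about 5% (equal), up to about 9% (unequal) |
| Week 4 and Week 8 rows, with treatment-by-week | unbiased | about 4–5.5% |

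**The case against.** The best defence is that the rows were always meant to be Week 4 and Week 8. A change score has no natural baseline row. The disputed sentence may only say when scores are collected and why a random intercept is used. Section 10.3.5 admits children with at least one Week 4 or Week 8 measurement, which fits post-baseline rows, and section 10.4 promises detail in the SAP. This has force: the documents do not show that the primary p-value and interval will be wrong. But nothing states that the baseline row is excluded, the sentence names it, and a contrast running from baseline to Week 8 invites a programmer to make baseline a level of assessment week.

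A reader might also infer that the effect shrinks and the Week 8 SE is too small in the same analysis. That does not follow. Shrinkage needs the model without treatment-by-week, where the SE is valid for what is estimated. The SE that is too small for a Week 8 level difference needs the model with that term, where nothing shrinks.

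Nor does the 8–12% error rate apply to the contrast the text names. That contrast holds about 5% under equal correlations. Its inflation under unequal ones comes from forcing a single correlation on three visits. Keeping the random intercept but dropping the baseline row largely removes it.

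**Conclusion.** The point holds as a defect in the wording whose effect depends on the coding. Taken literally, section 10.4.1 gives baseline ABC-H two incompatible roles, and each way of running it is worse than the simple alternative:

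- a diluted effect (5.4 becomes about 3.6 or 2.7);
- a Week 8 level test whose SE is about 13–20% too small; or
- a contrast that loses the baseline adjustment (SE 1.83 against 1.60 at correlation 0.5) and can reject up to about 9% of the time under the null.

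Only one of these can apply to a given analysis. The sizes rest on assumed visit correlations and Week 4 effects and on complete data. The 20% dropout and the ABC-H entry minimum of 18 were not simulated. The planned numbers of 48 and 60 are unaffected.

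**What to change.** In section 10.4.1 and in the SAP, before data lock:

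1. State that the response is change from baseline in ABC-H at Week 4 and Week 8 only.
2. State that baseline ABC-H enters only as a covariate, and delete the word *baseline* from the list of visits in the sentence on correlated scores.
3. Add treatment-by-week to the fixed effects.
4. Define the primary contrast as the GIR minus placebo difference at Week 8.

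Items 1 and 2 alone are not enough: without treatment-by-week the estimate is still about 4.05 for a true 5.4 when the Week 4 effect is half. The same wording should carry over to the Week 4 ABC-H endpoint and the continuous sleep scales. The cost is a few lines of text, with no new data, visits or patients.

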10.4.2 Secondary Analysis

Safety profile of GIR will be presented using AEs and solicited safety ESIs. Number of AEs, SAEs, and SUSARS will be summarized by treatment group (GIR vs. placebo) and overall, by severity, and by each Medical Dictionary for Regulatory Activities (MedDRA®) system organ class and preferred term.

Incidence of safety ESIs will also be presented by treatment group (GIR vs. placebo) and overall. Additional model based analyses of safety ESIs will be performed to estimate treatment effect adjusted for baseline covariates and cumulative dose.

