5.5.3 Study Investigator/Sponsor Decides to Withdraw Participant

The study doctors or sponsor may decide to take the participant out of this study without consent if:

- Participant's condition changes and the study is no longer in their best interest
- Participant/parent/legal guardian non-compliance with the study protocol
- The entire study is stopped by the FDA or the sponsor

A participant may be withdrawn from receiving study product if they experience a clinically significant AE that requires discontinuation of treatment, at the discretion of the study doctor or sponsor.

If any of the above occurs, the participant/parent/legal guardian will be informed and the investigator will discuss other options.

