6.8 Dose Escalation Assessments

Every 5 (+ 2) days through Week 7, just prior to each dose escalation assessment, parent/legal guardian will be asked to measure HR and BP using the device given to them from the study team at the time of randomization. A telephone or in-person assessment by the treating clinician will occur to determine dose escalation. If the participant reaches the maximum dose of 3 mg/day, prior to Week 7, no dose escalation will occur. Alternatively, a CGI-I will be determined by the treating clinician and any score of 3 or worse (higher) will warrant dose escalation, provided no significant safety concerns exist. AEs and safety ESIs will be recorded to assess safety.

Clinically significant findings that would prevent dose escalation include, but are not limited to:

- CGI-I score of 2 or 1
- HR and BP values that are considered unsafe to dose escalate:
 - Clinically significant hypotension, defined as systolic BP percentile less than the 5th percentile.^{31,34} This corresponds to systolic BP percentiles for neurotypical children under the 8th percentile for males and under the 10th percentile for females.
 - Clinically significant bradycardia, defined as HR > 2 SD below mean for age
- Any AEs or safety ESIs that make it unsafe to dose escalate, at the discretion of the treating clinician
- Any other finding that indicates it is not safe to dose escalate, at the discretion of the treating physician and/or principal investigator (PI).

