6.13 Dosage and Study Drug Information

6.13.1 Dose Timing

Dose escalation

Study product will be administered once daily (q.h.s.) during the first 5 (+ 2) days of study product administration and then twice daily thereafter. Twice daily doses may be administered in uneven BID dosing; for example, a total daily dose of 2.0 mg can be divided into 0.5 mg in the morning and 1.5 mg in the evening, at the discretion of the clinical provider. Dose escalation will occur based on the details in **Table 3** with the highest dose being dose level 6. Participants in both the GIR and placebo arms will be evaluated for potential dose escalation every 5 (+ 2) days via a Dose Escalation Assessment (via telephone during Weeks 1-3 and 5-7 or in-person at Week 4) described in Section **6.8**. Parent/legal guardian will be asked to measure HR and BP prior to each dose escalation assessment. If there is a safety concern during the weekly Dose Escalation Assessments (via telephone during Weeks 1-3 and 5-7 or in-person at Week 4) as stated in Section **6.8**, or for any other reason, the sites will be instructed on the following:

1. Hold at current dose/schedule for 5 (+ 2) days (or advance directly to step #3 or step #5 below, if deemed appropriate by the clinical provider)

2. Reassess at next dose-escalation assessment
3. If sedation is a significant concern, divide the total daily dose and give higher dose proportion at bedtime (q.h.s); example: 2 mg totally daily dose split as 0.5 mg in the morning and 1.5 mg q.h.s and
4. Reassess at next dose-escalation assessment
5. If safety concern remains, reduce total daily dose to the lower dose previously tolerated

Table 3. Dose Escalation Plan*

Dose Level	Total daily dose for weight \geq 25 kg (mg)
1	0.5
2	1.0
3	1.5
4	2.0
5	2.5
6	3.0

* Parent/legal guardian will be asked to measure HR and BP prior to each dose escalation assessment.

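### Section 10.4.2 adjusts the ESI treatment effect for cumulative dose, which is set after randomization and partly by the ESIs themselves, so the arm coefficient is not the randomized effect of GIR

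*Combined protocol and SAP*

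**What the plan says.** Safety is the secondary objective (Section 3), and incidence of safety ESIs is one of its endpoints (Section 10.2.2). Section 10.4.2 plans two ESI analyses. The first is descriptive: "Incidence of safety ESIs will also be presented by treatment group (GIR vs. placebo) and overall". The second is a model: "Additional model based analyses of safety ESIs will be performed to estimate treatment effect adjusted for baseline covariates and cumulative dose". The model is a commitment, its stated target is the treatment effect, and it is the only model-based ESI treatment estimate the plan commits to.

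Elsewhere the protocol sets out how dose is determined:

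- Section 6.13.1: "Participants in both the GIR and placebo arms will be evaluated for potential dose escalation". Placebo is titrated under the same masked rules as GIR.
- Section 6.8 lists findings that prevent escalation. They include "CGI-I score of 2 or 1" and "Any AEs or safety ESIs that make it unsafe to dose escalate, at the discretion of the treating clinician".
- Section 6.13.1, as the last step of its safety sequence: "If safety concern remains, reduce total daily dose to the lower dose previously tolerated".
- Section 5.5.3: "A participant may be withdrawn from receiving study product if they experience a clinically significant AE that requires discontinuation of treatment".

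Section 7.1.2 has ESIs solicited at the dose-escalation assessments, the contacts at which dose is decided. The documents do not define cumulative dose for a placebo child, and they give no cut-off for dose relative to the ESI. Section 10.4 defers detail to an SAP to be written before data lock.

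**The concern.** Randomization protects the comparison of arms as long as the model conditions only on what was fixed beforehand. Cumulative dose fails that test in three ways. It lies on the path from GIR to a dose-related ESI. The ESI changes it. It also depends on CGI-I response, which GIR is meant to improve. Comparing arms at equal cumulative dose therefore compares children selected by what happened to them on treatment.

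The result would be labelled a treatment effect and would sit beside the by-arm incidence, with no rule for which to believe if they disagree. Depending on coding and event rates, a real dose-related ESI could appear weak, or an absent effect could appear as harm.

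**Working it through.** **1. The plan's own figures.** The plan states no figure for the ESI model. Its only sample-size figure concerns the primary endpoint and is not touched: 32 vs 16 (2:1), d = 0.9, two-sided 0.05 gives power 0.82 by noncentral t, and 48/0.8 = 60.

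**2. Range of the covariate** (Table 3 levels of 0.5 to 3.0 mg/day; 56 days; full adherence).

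- Never escalated: 0.5 × 56 = 28 mg.
- Escalated every 5 days: 5 × (0.5 + 1 + 1.5 + 2 + 2.5) + 31 × 3 = 37.5 + 93 = 130.5 mg.
- Escalated every 7 days: 7 × 7.5 + 21 × 3 = 52.5 + 63 = 115.5 mg.

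The spread is 130.5/28 = 4.7-fold, and titration decides where a child falls in it.

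**3. What the arm coefficient means.** Write logit P(ESI) = b0 + b1·arm + b2·dose.

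- *Dose in mg, placebo = 0.* b1 is the GIR log-odds extrapolated to 0 mg, minus the placebo log-odds. Zero lies below the whole full-adherence range. A positive dose slope within GIR (dose-driven harm) pulls b1 down. A negative slope (ESIs cut dose) pushes it up. The direction depends on which dominates.
- *Dose in capsules, both arms.* b1 compares arms at equal capsule count, that is, conditional on titration that outcomes partly drove.
- *mg centred within GIR.* b1 is GIR at its mean dose against placebo. It stays close to the unadjusted value, so the covariate adds nothing to the treatment effect.

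**4. Correlation of arm and dose, placebo = 0 mg.** With share p on GIR, r² = 1/(1 + CV²/(1 − p)); at p = 2/3 this is 1/(1 + 3·CV²). Section 10.6 reports that doses in an earlier single-arm study "were 1.1 (± 0.5) mg/day, reflecting the more conservative approach to dose escalation in this patient population with DS". I assume that the 0.5 is an SD and that cumulative dose has the same CV: 0.5/1.1 = 0.4545. Then r² = 1/1.620 = 0.617, r = 0.79, VIF = 1/(1 − 0.617) = 2.61, and the SE rises √2.61 = 1.62-fold (linear-model formula). For an assumed CV of 0.2 to 0.5, r is 0.95 to 0.76 and the SE rises 3.1- to 1.5-fold.

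**5. Illustration by simulation.** All rates are assumed; the results are not bounds. Two sets follow the titration rules over 11 five-day periods, 300,000 children, 2:1. Entries are arm odds ratios for any ESI.

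Set 1: log-normal frailty, SD 0.8; persistent response per period 0.04 on placebo and 0.08 on GIR; ESI hazard per period 0.05 in both arms (null), or 0.022 plus 0.8 log-hazard per mg on GIR (dose-driven). In the middle case, 50% of ESIs block escalation and 25% lower the dose.

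| Set 1, middle case | ESI, GIR vs placebo | Unadjusted | mg, placebo 0 | Capsules | mg centred |
|---|---|---|---|---|---|
| Null | 37% vs 37% | 1.0 | 1.7 | 0.94–0.96 | 1.0 |
| Dose-driven | 62% vs 20% | 6.5 | 1.5 | 7.7 | 6.6 |

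- No feedback from ESIs to dose: the null is undistorted (1.00–1.03); dose-driven harm with mg is 0.8 against 6.5 unadjusted.
- Every ESI blocks and lowers dose: dose-driven harm is 3.8 with mg and 6.7 with capsules, against 6.5 unadjusted. That is attenuation, not a null.
- 10–20% of ESIs also stop the drug, null: 1.9–3.8 with mg, 0.86–0.94 with capsules.

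Set 2: logistic ESI model with between-child SD 1; every ESI blocks escalation and half lower the dose; except in the last row, CGI-I response rises with GIR dose (1.2 log-odds per mg).

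| Set 2 | Unadjusted | Capsules | mg, placebo 0 |
|---|---|---|---|
| Null on ESIs | 1.00 | 0.56 | 22.5 |
| +0.5 log-odds per mg | 2.87 | 1.81 | 24.0 |
| +0.8 log-odds per mg | 5.73 | 3.79 | 26.8 |
| +0.5 per mg, no CGI-I effect | 3.37 | 3.26 | about 10,000 |

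The last mg entry is pure extrapolation to zero dose. With the same coding, Set 1 mostly hides dose-driven harm and Set 2 inflates it.

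**6. At N = 60 (40:20), 2,000 replicates.** In Set 1's middle dose-driven case, harm is detected in 91% of trials unadjusted, 92% with capsules and 4% with mg and placebo = 0. In Set 2's null, rejection is 5.2%, 13.7% and 36.6% in the same order. The 4% belongs to the placebo = 0 mg coding under these rates and to nothing else.

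**The case against.** The strongest reply is that little hangs on this model. The secondary endpoint is ESI incidence, and that is presented by arm without adjustment. The model is described as additional, and it carries no hypothesis, power claim or halting rule. The wording discloses the adjustment and does not call the result an intention-to-treat effect. The promised SAP could settle the coding. With capsule coding, natural when both arms take masked titrated capsules, most simulated cases show modest distortion. Relating ESIs to dose is also a sensible clinical question.

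Much of this stands. The randomized ESI comparison is not lost, and that limits the damage. Capsule coding is far less harmful than mg with placebo at zero, although Set 2 shows it is not safe in general (0.56 under a true null).

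The objection does not remove the point. The stated target is the treatment effect, and none of the three codings makes the dose covariate help to estimate it. The interest in dose is a separate question. Section 10.4.3 does not firmly cover it, because the exposure-response analysis there is optional and uses PK exposure.

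**Conclusion.** The point holds and should be corrected before data lock. The arm coefficient from the planned ESI model is not the randomized effect of GIR. That follows from the titration and withdrawal rules alone and needs no assumed rate. Size and direction do need assumptions that the documents do not supply: event rates, how often ESIs alter dose, whether harm is dose-driven, and how placebo dose is coded. The document-based figures are the 28 to 130.5 mg range and, with the CV assumption above, r of about 0.79 and an SE increase of about 1.6-fold.

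Three stronger readings are tempting and are not supported:

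- *The plan will hide dose-related harm.* A reader might infer this from the 4% detection rate. Masking in the simulations arises only with placebo coded as 0 mg, it is partial under strong feedback, and other rates give inflation under the same coding. The by-arm incidence would still show the difference.
- *Arm and dose are nearly collinear.* The spread quoted in Section 10.6 gives substantial correlation, not near-collinearity.
- *The efficacy models share the flaw.* In Section 10.4.1, cumulative dose stands only in a list of optional covariate analyses, apart from the committed fixed effects. The later reference to covariates already identified ordinarily means the committed set. The primary analysis and sample size are unaffected.

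**What to change.** In Section 10.4.2, or in the SAP due before data lock, remove cumulative dose from the model that estimates the ESI treatment effect. Suggested wording: *The effect of GIR on each safety ESI will be estimated by randomized arm with a 95% confidence interval, unadjusted or adjusted for named pre-randomization covariates only.*

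If a look at dose is wanted, add a separate table labelled descriptive and non-causal: ESIs by the dose level in force during the assessment interval in which the ESI was reported, for GIR and for placebo at the same capsule level. The assessment interval is used because Sections 7.1.2 and 7.5 describe yes/no solicitation at assessments and mention no onset date; a table by dose before onset would need one.

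The cost is wording and one optional table. Sample size, dosing and Section 10.4.1 need no change. The table would have small cells (60 × 2/3 = about 40 GIR children over six levels) and would still be shaped by titration, so it should not be read as a dose-response estimate. The planned dose-adjusted treatment effect would no longer be reported.
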